5.4 Secondary statistical analyses

Secondary outcomes will be evaluated in the full analysis set according to ITT. Secondary statistical analyses are intended to be exploratory (hypothesis generating) and will be interpreted accordingly. A two-sided p-value of ≤ 0.05 will be considered as noticeable (“significant”) without adjustment for multiplicity.

Statistical analysis of the pre-specified secondary endpoints will be performed with descriptive and inferential statistical methods. In inferential statistical analyses two-sided significance tests will be applied with a local significance level $\alpha=0.05$. All point estimates of parameters of interest will be supplemented by 95% confidence intervals unless otherwise stated.

Secondary outcomes will be evaluated and compared between the randomized treatment arms with stratification by center using the following methods. In case of normally or non-normally distributed metric outcomes, a two-way ANOVA or the van Elteren test will be applied, respectively. Categorical outcomes will be analyzed using (generalized) Cochrane Mantel Haenszel tests. Survival data will be analysed using the Kaplan-Meier method and the stratified log-rank test. Hazard ratios will be estimated based on stratified Cox proportional hazards models after checking the proportional hazards assumption based on the Schoenfeld residuals.

The duration of RRT will be evaluated in two ways.

1. If a patient dies or reaches his/her end of follow-up, the duration of RRT is finished.
2. In a competing risk analysis, besides the event of interest end of RRT, death (while RRT otherwise would be ongoing) is considered a competing event. If a patient reaches his/her end of follow-up, the duration of RRT is censored.

The duration of hospital stay will be evaluated in two ways.

1. If a patient dies or reaches his/her end of follow-up, the hospital stay is finished.
2. In a competing risk analysis, besides the event of interest end of hospital stay, death (while hospital stay otherwise would be ongoing) is considered a competing event. If a patient reaches his/her end of follow-up, the duration of hospital stay is censored.

The duration of ICU stay will be evaluated in two ways.

1. If a patient dies or reaches his/her end of follow-up, the ICU stay is finished.

² A one-sided version of the Cochrane Mantel Haenszel test (CMH) is constructed, using the fact that the CMH test statistic – if it is not squared – follows a standard normal distribution under the null hypothesis $H_0: AKI_1=AKI_0$ (in all strata).

2. In a competing risk analysis, besides the event of interest end of ICU stay, death (while ICU stay otherwise would be ongoing) is considered a competing event. If a patient reaches his/her end of follow-up, the duration of ICU stay is censored.

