3.2 Secondary endpoints

1. Adherence to the KDIGO bundle
2. Occurrence and severity of any stage of acute kidney injury within 3 days after surgery
3. Change in biomarker values during 12 hours after initial measurement of [TIMP2]*[IGFBP7]
4. Free-days of mechanical organ support through to day 3
5. Free-days of vasopressors through day 3
6. Need of RRT at day 30 and 90
7. Duration of RRT at day 30 and 90
8. Renal recovery at day 90
9. 30-day and 90-day mortality
10. ICU length-of-stay and Hospital length-of-stay
11. Major adverse kidney events (MAKE90) (defined as the composite of death, use of RRT and persistent renal dysfunction (defined as serum creatinine $\geq 2x$ to baseline value at hospital discharge)) at day 90

4 Statistical Analyses

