5.1 Randomization and Blinding

Treatment assignment will be accomplished using REDCap and randomization will be performed centrally in a 1:1 proportion, stratified by center. Patients will enter the observation period immediately after randomization.

Neither the patient, nor the study personnel can be blinded in regards to the treatment assignment. The individuals involved in adjudication of endpoints or complications will be blinded to treatment assignment.

Randomization will be checked by comparing demographical and clinical baseline variables between the randomized groups. Differences between treatment groups will be quantified as follows.

1. Normally distributed continuous variables:
Student's two-sample t test, absolute mean difference between groups
2. Non-normally distributed continuous variables:
Wilcoxon two-sample test (t approximation), Hodges-Lehmann estimator of location shift
3. Categorical variables: Absolute difference of percentages, odds ratio
4. Censored variables: Absolute difference of percentages, hazard ratio

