If the p-value of the one-sided null hypothesis $H_{0b}: AKI_1 \leq AKI_0$ is $p_b^{interim} \leq 0.0015$, the trial is finished. It will be concluded that the primary endpoint rate under the interventional treatment AKI_1 is higher than under standard care (AKI_0), and that the interventional treatment is inferior to standard care.

If either $p_a^{interim} \leq 0.0015$ or $p_b^{interim} \leq 0.0015$, recruitment will stop as soon as possible. The primary final analysis will be performed with all patients who have been included in the interim analysis. Additional sensitivity analyses will be performed, additionally including "interim patients" who have been recruited between the data base lock of the interim analysis and the final recruitment stop.

If both p-values of the one-sided null hypotheses $H_{0a}: AKI_1 \geq AKI_0$ and $H_{0b}: AKI_1 \leq AKI_0$ are > 0.0015 , the trial will be continued and the following procedure will be applied.

Let p_a^{interim} denote the p-value of the one-sided null hypothesis $H_{0a}: AKI_1 \geq AKI_0$ in the interim analysis. Based on p_a^{interim} the number of additional evaluable patients n_2 (recruited after the interim analysis) will be determined as follows.

- If $p_a^{\text{interim}} \leq 0.0015$, the trial is finished after the interim analysis (see above).
- If $0.0015 < p_a^{\text{interim}} \leq \alpha_{\text{interim}}$,
an additional number of $n_2=2 \times 250=500$ evaluable patients will be recruited.
The final statistical analysis will be performed using data of $n_2=2 \times 250=500$ additional patients, who were recruited after the interim analysis.
The total number of evaluable patients is $n_1+n_2 = 618+500 = 1118$ (559 patients per treatment group).
- P-values in the range $p_a^{\text{interim}} > \alpha_{\text{interim}}$ include those with $p_a^{\text{interim}} > 0.5$. P-values $p_a^{\text{interim}} > 0.5$ occur when in the interim analysis the observed primary endpoint rate under the interventional treatment AKI_1 is higher than under standard care (AKI_0), indicating that the interventional treatment is inferior to standard care.
If $p_a^{\text{interim}} > \alpha_{\text{interim}}$ (or even >0.5),
an additional number of $n_2=2 \times 400=800$ evaluable patients will be recruited.
The final statistical analysis will be performed using data of $n_2=2 \times 400=800$ additional patients, who were recruited after the interim analysis.

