The total number of evaluable patients is $n_1+n_2 = 618+800 = 1418$ (709 patients per treatment group).

The parameter α_{interim} was specified at the time when the present Statistical Analysis Plan (SAP) was written (12 May 2023). Since then, its value is finally determined and will not be changed. The specified value of α_{interim} however is not included in the present SAP. It must be kept confidential until the end of the trial, in order to preserve the integrity of the trial. An appendix to the SAP was written at the same time as the present SAP (12 May 2023). The appendix to the SAP contains the specified value of α_{interim} . The appendix to the SAP is sent to the Data Safety Monitoring Board (DSMB). The DSMB deposits the appendix to the SAP until the end of the trial. It guarantees that the appendix to the SAP is not assessed by the Principal Coordinating Investigator or any other study personell. After the end of the trial, the DSMB will check and confirm that the trial was conducted applying the previously specified value of α_{interim} .

If the trial is continued after the interim analysis, the information about the further recruitment will be reported to the Principal Coordinating Investigator and all other study personell in a stepwise way. That means after the interim analysis in a first step the Principal Coordinating Investigator will be informed only, if the trial will be finished after the interim analysis ($n_2=0$), or if it will be continued. If the trial is continued, in the first step the Principal Coordinating Investigator will not get to know the sample size n_2 yet. If the sample size n_2 is $n_2=500$ or $n_2=800$, will be reported to the Principal Coordinating Investigator only in a second step, at the time when additional 500 evaluable patients have been recruited. At that time, the Principal Coordinating Investigator will be informed, if the final sample size is reached ($n_2=500$), or if recruitment will be continued up to additional 300 evaluable patients (so that $n_2=500+300=800$).

In the final statistical analysis, data of n_2 additional patients will be evaluated, who were recruited after the interim analysis ($n_2=500$ or $n_2=800$, see above).

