5.7 Operating characteristics

The operating characteristics of the applied design and sample size adaptation are shown below, including the total numbers of patients, percent stops after stage 1, and overall power. The operating characteristics were determined with the R software (RPACT package) in 1000000 simulation runs. Simulated data were generated assuming equal primary endpoint rates across all strata under standard care ($AKI_0=20\%$ in all strata), as well as under the interventional treatment ($AKI_1=10\%/14\%/15\%$ in all strata). The statistical analysis of simulated data was performed with Pearson's chi-squared tests.

Expected primary endpoint rate under standard care AKI_0	20%	20%	20%	20%
Expected primary endpoint rate under the interventional treatment AKI_1	10%	14%	15%	20%
Total number of patients:				
1. Minimum	618	618	618	618
2. Average	772.8	1145.1	1222.8	1400.8
3. Maximum	1418	1418	1418	1418
Percent stops after stage 1	70.8%	16.3%	9.1%	0.3%
Overall power (rejection of H_{0a})	99.9%	82.1%	66.0%	2.5%

6 Treatment of missing values

Missing values that may arise in effectiveness or safety parameters will not be replaced by any kind of statistical imputation.

7 Software

Statistical analyses will be performed using the statistical software SAS.

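### The 12-hour change in [TIMP2]*[IGFBP7] is compared with center as the only adjustment; adding the initial value could recover precision at almost no cost.

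*SAP*

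**What the plan says.** SAP section 3.2 lists as the third secondary endpoint "Change in biomarker values during 12 hours after initial measurement of [TIMP2]*[IGFBP7". A patient therefore has a value for this endpoint only if the initial measurement exists.

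Section 5.4 gives the general rule: "Secondary outcomes will be evaluated and compared between the randomized treatment arms with stratification by center using the following methods". For metric outcomes it continues: "In case of normally or non-normally distributed metric outcomes, a two-way ANOVA or the van Elteren test will be applied, respectively". Special rules follow for the duration of RRT, hospital stay and ICU stay, but none for the biomarker. No section names the initial biomarker value as a covariate. Section 5.4 also calls the secondary analyses exploratory and states: "All point estimates of parameters of interest will be supplemented by 95% confidence intervals unless otherwise stated".

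Three further statements bear on the point. Section 5.1 says that "randomization will be performed centrally in a 1:1 proportion, stratified by center". Section 6 says: "Missing values that may arise in effectiveness or safety parameters will not be replaced by any kind of statistical imputation". Section 5.6 gives the final sizes if the trial continues after the interim analysis: "559 patients per treatment group" or "709 patients per treatment group".

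**The concern.** A change score subtracts the whole initial value from the later one, which amounts to fixing the regression slope on the initial value at 1. If the true slope differs from 1, part of the spread in the initial values stays in the change as noise. A model that includes the initial value estimates the slope and removes that noise.

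At stake is the width of the confidence interval on the ANOVA path, and the power of the test on the van Elteren path. Validity is not at stake: with randomized arms, the center-stratified comparison of changes is unbiased. The primary endpoint, its alpha and the sample size are untouched.

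**Working it through.** **The plan's own figures.** The SAP states no power or precision for this endpoint. Its only design figures concern the primary endpoint, and they reproduce. With 20% against 14%, 309 per arm per stage and bounds 2.963 and 1.969, stage 1 power is 0.163 (stated 0.1647) and overall power 0.801 (stated 0.8010). For recruitment, 1236/0.95 = 1301.1, rounded up to 1302 as stated.

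**Inputs.** 1:1 allocation comes from section 5.1, and 559 or 709 per arm from section 5.6. Those sizes were set for the primary endpoint and are used here as an approximation. Not in the SAP, and therefore assumed: the correlation rho of the initial and 12-hour values, the ratio k of the 12-hour SD to the initial SD, and the form of the change. A simple difference is taken. The formula does not apply to percentage change; for a log ratio, rho and k refer to logged values.

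**ANOVA path.** In units of the initial SD, the residual variance per patient is

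- change score: 1 + k² − 2·rho·k
- adjusted for the initial value: k²(1 − rho²)

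The first minus the second is (1 − k·rho)². This is never negative, and it is zero only when k·rho = 1. The variance ratio, adjusted over change score, is k²(1 − rho²)/(1 + k² − 2·rho·k):

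| k | rho 0.3 | rho 0.5 | rho 0.7 | rho 0.9 |
|---|---|---|---|---|
| 0.75 | 0.46 | 0.52 | 0.56 | 0.50 |
| 1 | 0.65 | 0.75 | 0.85 | 0.95 |
| 1.5 | 0.87 | 0.96 | 1.00 | 0.78 |
| 2 | 0.96 | 1.00 | 0.93 | 0.54 |

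The interval width scales with the square root of the ratio. From √0.46 = 0.68 to √1.00 = 1, the interval is 32% to 0% narrower. At k = 1 it is 19%, 13%, 8% and 3% narrower.

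Half-widths at k = 1, in initial SDs, are 1.96·√((2/n)·2(1 − rho)) for the change score and 1.96·√((2/n)(1 − rho²)) after adjustment:

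| rho | n = 559: change / adjusted | n = 709: change / adjusted |
|---|---|---|
| 0.3 | 0.139 / 0.112 | 0.123 / 0.099 |
| 0.5 | 0.117 / 0.102 | 0.104 / 0.090 |
| 0.7 | 0.091 / 0.084 | 0.081 / 0.074 |
| 0.9 | 0.052 / 0.051 | 0.047 / 0.045 |

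Simulation agrees. With 1118 patients, 20 assumed centers and 1500 runs, the variance ratios at k = 1 were 0.62, 0.73, 0.88 and 0.95. A second simulation with 30 assumed centers gave type I error of 5.0% to 5.9% without the covariate and 5.3% to 6.5% with it (simulation error about 0.6 points).

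**Cost if the covariate is useless.** One degree of freedom. With N patients and 30 assumed centers, variance rises by a factor of about 1 + 1/(N − 33): 1.0017 at N = 618 and 1.0007 at N = 1418.

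**Van Elteren path.** Simulated with 20 assumed centers of 56 patients, 10,000 runs per setting and an assumed shift of 0.15·k. The efficiency ratio is (mean z of van Elteren / mean z of rank ANCOVA)²; below 1 favors rank ANCOVA. The lognormal case assumes a log SD of 0.8 for the initial value, sets rho, k and the shift on the log scale, and analyzes the raw difference.

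| k; rho | Normal | Lognormal |
|---|---|---|
| 1; 0.3 / 0.5 / 0.7 / 0.9 | 0.69 / 0.77 / 0.87 / 0.96 | 0.69 / 0.77 / 0.85 / 0.92 |
| 0.75; 0.5 | 0.56 | 0.58 |
| 1.5; 0.3 / 0.5 | 0.89 / 0.97 | 0.86 / 0.94 |
| 2; 0.5 | 1.00 | 0.99 |

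Type I error at nominal 5% was 0.046 to 0.055 for both tests. In the lognormal case at k = 1 and rho 0.5, power was 0.61 for van Elteren and 0.72 for rank ANCOVA.

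**The case against.** The SAP names a valid, center-stratified method for one of 11 exploratory endpoints. Preferring a more efficient valid method comes close to taste, and no decision in the trial depends on it. This stands, and it limits the weight of the point. Still, adjustment loses nothing in large samples on the ANOVA path, so the choice is not evenly balanced.

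The size of the gain rests on assumptions. The 32% occurs only at k = 0.75. At k = 1.5 or 2 with rho 0.3 to 0.7, the ratios are 0.87 to 1.00 and the interval is 0% to 7% narrower. This stands too: no single figure should be read as the expected gain.

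Section 1.1 describes a biomarker-guided approach. If enrolment required a high initial value (an inference; the SAP gives no cutoff), the initial SD would shrink and k would rise. Take normal data with equal SDs before selection and keep the upper half of initial values. Their variance falls to 1 − 2/π = 0.363, and the ratio becomes (1 − rho²)/((1 − rho²) + 0.363(1 − rho)²). At rho 0.3, 0.5 and 0.7 before selection this is 0.84, 0.89 and 0.94, so the interval is 8.5%, 5.6% and 3.1% narrower instead of 19%, 13% and 8%. That lowers the k = 1 figures for the ANOVA path but stays within the stated range and still favors adjustment. For the rank test on lognormal data, the same selection left the ratios nearly unchanged (0.67, 0.76 and 0.85).

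On the non-normal path, rank ANCOVA gives only a p-value, so no interval narrows there. This is correct, and the interval argument is confined to the ANOVA path. The main rank simulations used equal centers. A further lognormal simulation with small, unequal centers, with and without such selection, gave efficiency ratios of 0.64 to 0.95 and type I error of about 4% to 6%, so the result does not depend on equal center sizes.

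**Conclusion.** The point holds as an optional improvement. Center is the only adjustment for this endpoint, and a useful covariate is on hand for every patient who has a change value. Since nothing is imputed, adjustment excludes no one whom the planned analysis would include.

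The gain may be substantial or nil. It vanishes when k·rho = 1, and the SAP does not allow it to be narrowed further. The range rests on assumed rho and k, on reading the change as a simple difference and, for the rank test, on assumed center numbers and distributions.

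**What to change.** For secondary endpoint 3 only, add one sentence for each planned path to SAP section 5.4, before unblinded data are seen:

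- *Normal path:* the change is analyzed by the planned ANOVA with arm and center, with the initial [TIMP2]*[IGFBP7] value added as a covariate; the adjusted difference in change is reported with its 95% confidence interval.
- *Non-normal path:* the change is compared by a center-stratified rank ANCOVA, with change and initial value ranked within center, in place of the plain van Elteren test.

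Both keep the listed endpoint as the outcome. The text should also say whether the change is a difference, a percentage or a ratio. A log-scale model would target relative change and should be supplementary at most.

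The cost is two sentences, one degree of freedom on the first path and one replaced test on the second. Naming the covariate in advance also rules out a later choice between adjusted and unadjusted results.

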5.5 Sample size calculation

Sample size and power calculations are based on a group sequential adaptive plan with one interim analysis and the primary endpoint occurrence of moderate or severe AKI (KDIGO stage 2 or 3) within 72 hours after surgery. The expected AKI rate (\geq stage 2), substantiated by published data of the BigpAK trial, in the control group and the intervention group is 20% and 14%, respectively. The interim analysis will be performed when 309 evaluable patients have been recruited in each treatment group ($2 \times 309 = 618$ patients in total). Using the results of the interim analysis, the sample size of the final analysis will be recalculated (see below). If no sample size adjustment is found to be necessary, the final analysis will be performed when additional 309 evaluable patients have recruited in each treatment group after the interim analysis ($2 \times 309 + 2 \times 309 = 1236$ evaluable patients in total). A number of up to 5% of recruited patients are expected to be lost to follow up and in the worst case have completely non-evaluable data. Therefore, a total number of 1302 patients will be recruited in order to provide a number of 1236 evaluable patients.

The characteristics of the group sequential adaptive plan for the one-sided tests are shown below.

Information rate	bounds accept H_0	bounds reject H_0	sign.level one-sided	α spent	β spent	power achieved	stage n_1	sizes n_2
0.5	-	2.963	0.0015	0.0015	-	0.1647	309.0	309.0
1.0	1.969	1.969	0.0245	0.0250	-	0.8010	309.0	309.0

Calculations were performed using the ADDPLAN software.

5.6 Primary statistical analysis: Details of the interim analysis, sample size adaptation and final analysis

The interim analysis will be performed using data of $n_1 := 2 \times 309 = 618$ evaluable patients (309 patients per treatment group).

If the p-value of the one-sided null hypothesis $H_{0a}: AKI_1 \geq AKI_0$ is $p_a^{interim} \leq 0.0015$, the trial is finished. It will be concluded that the primary endpoint rate under the interventional treatment AKI_1 is lower than under standard care (AKI_0), and that the interventional treatment is superior to standard care.

If the p-value of the one-sided null hypothesis $H_{0b}: AKI_1 \leq AKI_0$ is $p_b^{interim} \leq 0.0015$, the trial is finished. It will be concluded that the primary endpoint rate under the interventional treatment AKI_1 is higher than under standard care (AKI_0), and that the interventional treatment is inferior to standard care.

If either $p_a^{interim} \leq 0.0015$ or $p_b^{interim} \leq 0.0015$, recruitment will stop as soon as possible. The primary final analysis will be performed with all patients who have been included in the interim analysis. Additional sensitivity analyses will be performed, additionally including "interim patients" who have been recruited between the data base lock of the interim analysis and the final recruitment stop.

If both p-values of the one-sided null hypotheses $H_{0a}: AKI_1 \geq AKI_0$ and $H_{0b}: AKI_1 \leq AKI_0$ are > 0.0015 , the trial will be continued and the following procedure will be applied.

Let p_a^{interim} denote the p-value of the one-sided null hypothesis $H_{0a}: AKI_1 \geq AKI_0$ in the interim analysis. Based on p_a^{interim} the number of additional evaluable patients n_2 (recruited after the interim analysis) will be determined as follows.

- If $p_a^{\text{interim}} \leq 0.0015$, the trial is finished after the interim analysis (see above).
- If $0.0015 < p_a^{\text{interim}} \leq \alpha_{\text{interim}}$,
an additional number of $n_2=2 \times 250=500$ evaluable patients will be recruited.
The final statistical analysis will be performed using data of $n_2=2 \times 250=500$ additional patients, who were recruited after the interim analysis.
The total number of evaluable patients is $n_1+n_2 = 618+500 = 1118$ (559 patients per treatment group).
- P-values in the range $p_a^{\text{interim}} > \alpha_{\text{interim}}$ include those with $p_a^{\text{interim}} > 0.5$. P-values $p_a^{\text{interim}} > 0.5$ occur when in the interim analysis the observed primary endpoint rate under the interventional treatment AKI_1 is higher than under standard care (AKI_0), indicating that the interventional treatment is inferior to standard care.
If $p_a^{\text{interim}} > \alpha_{\text{interim}}$ (or even >0.5),
an additional number of $n_2=2 \times 400=800$ evaluable patients will be recruited.
The final statistical analysis will be performed using data of $n_2=2 \times 400=800$ additional patients, who were recruited after the interim analysis.
The total number of evaluable patients is $n_1+n_2 = 618+800 = 1418$ (709 patients per treatment group).

The parameter α_{interim} was specified at the time when the present Statistical Analysis Plan (SAP) was written (12 May 2023). Since then, its value is finally determined and will not be changed. The specified value of α_{interim} however is not included in the present SAP. It must be kept confidential until the end of the trial, in order to preserve the integrity of the trial. An appendix to the SAP was written at the same time as the present SAP (12 May 2023). The appendix to the SAP contains the specified value of α_{interim} . The appendix to the SAP is sent to the Data Safety Monitoring Board (DSMB). The DSMB deposits the appendix to the SAP until the end of the trial. It guarantees that the appendix to the SAP is not assessed by the Principal Coordinating Investigator or any other study personell. After the end of the trial, the DSMB will check and confirm that the trial was conducted applying the previously specified value of α_{interim} .

If the trial is continued after the interim analysis, the information about the further recruitment will be reported to the Principal Coordinating Investigator and all other study personell in a stepwise way. That means after the interim analysis in a first step the Principal Coordinating Investigator will be informed only, if the trial will be finished after the interim analysis ($n_2=0$), or if it will be continued. If the trial is continued, in the first step the Principal Coordinating Investigator will not get to know the sample size n_2 yet. If the sample size n_2 is $n_2=500$ or $n_2=800$, will be reported to the Principal Coordinating Investigator only in a second step, at the time when additional 500 evaluable patients have been recruited. At that time, the Principal Coordinating Investigator will be informed, if the final sample size is reached ($n_2=500$), or if recruitment will be continued up to additional 300 evaluable patients (so that $n_2=500+300=800$).

In the final statistical analysis, data of n_2 additional patients will be evaluated, who were recruited after the interim analysis ($n_2=500$ or $n_2=800$, see above).

The final overall p-value p_a^{final} of the one-sided null hypothesis $H_{0a}: AKI_1 \geq AKI_0$ is defined as the minimal possible one-sided significance level, that could have been specified, so that the final statistical analysis would result in rejection of the null hypothesis $H_{0a}: AKI_1 \geq AKI_0$ against the one-sided alternative $H_{1a}: AKI_1 < AKI_0$. If the final overall p-value is $p_a^{\text{final}} \leq 0.025$, it will be concluded that the primary endpoint rate under the interventional treatment AKI_1 is lower than under standard care (AKI_0), and that the interventional treatment is superior to standard care. The final overall p-value p_b^{final} of the one-sided null hypothesis $H_{0b}: AKI_1 \leq AKI_0$ is defined as the minimal possible one-sided significance level, that could have been specified, so that the final statistical analysis would result in rejection of the null hypothesis $H_{0b}: AKI_1 \leq AKI_0$ against the one-sided alternative $H_{1b}: AKI_1 > AKI_0$. If the final overall p-value is $p_b^{\text{final}} \leq 0.025$, it will be

concluded that the primary endpoint rate under the interventional treatment AKI_1 is higher than under standard care (AKI_0), and that the interventional treatment is inferior to standard care. The final overall two-sided p-value p^{final} is defined as the minimum of the doubled one-sided p-values p_a^{final} and p_b^{final} , i.e. $p^{final} = \min(2 \cdot p_a^{final}, 2 \cdot p_b^{final})$.

All reported numbers of patients refer to patients with evaluable primary endpoint data. The corresponding numbers of recruited patients may be increased in order to compensate for missing data.

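### Section 5.5 plans for 1236 evaluable and 1302 recruited patients, but under the rule in 5.6 a continuing trial ends at 1118 or 1418 evaluable patients

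*SAP*

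**What the plan says.** Section 5.5 sizes the trial for event rates of 20% under standard care and 14% under the intervention, with an interim analysis at 309 evaluable patients per group. It announces a recalculation at the interim and then describes the unadjusted case: "If no sample size adjustment is found to be necessary, the final analysis will be performed when additional 309 evaluable patients have recruited" in each group, 1236 in total. After allowing for up to 5% loss it concludes: "Therefore, a total number of 1302 patients will be recruited in order to provide a number of 1236 evaluable patients".

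Section 5.6 gives the rule. The trial stops at 618 if either one-sided interim p-value is at most 0.0015. Otherwise the p-value for superiority is compared with a confidential threshold. At or below the threshold, 250 more per group are recruited: "The total number of evaluable patients is $n_1+n_2 = 618+500 = 1118$ (559 patients per treatment group"). Above it, 400 more per group are recruited: "The total number of evaluable patients is $n_1+n_2 = 618+800 = 1418$ (709 patients per treatment group").

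The stepwise disclosure in 5.6 follows the same two sizes. When 500 additional evaluable patients are in, the coordinating investigator learns whether the final size has been reached, "or if recruitment will be continued up to additional 300 evaluable patients (so that $n_2=500+300=800"). For the final analysis, "data of n_2 additional patients will be evaluated, who were recruited after the interim analysis ($n_2=500$ or $n_2=800$, see above"). Section 5.6 ends with a general provision: "The corresponding numbers of recruited patients may be increased in order to compensate for missing data".

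**The concern.** The two sections disagree on how large the trial can be. Section 5.5 describes an unadjusted outcome with a second stage of 2 × 309 = 618 patients. Section 5.6 assigns every continuing trial to 500 or 800, and no interim result counts as needing no adjustment.

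The figure of 1302 is the only recruitment total the SAP prints, and it is stated without a condition. Anyone who takes the target from 5.5 (for site planning, supply, funding or a registry entry) works to a number that belongs to neither branch. Section 5.5 also shows 80.1% as the power, which is the power of a plan that will not be carried out.

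**Working it through.** **Inputs.** From 5.5: 309 per group at stage 1, 309 per group at stage 2 if unadjusted, loss up to 5%, rates 20% and 14%, bounds 2.963 and 1.969, power 0.8010. From 5.6: second-stage totals of 500 or 800. From 5.7 at 14% versus 20%: average total 1145.1, stops after stage 1 16.3%, power 82.1%.

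**Step 1: reproduce the 5.5 figures.**
- O'Brien-Fleming-type spending at information 0.5 and 1.0, one-sided 0.025, gives bounds 2.963 and 1.969.
- The equal-weight inverse normal test with 309+309 per group gives power 0.801. The stage 1 stopping probability is 0.163, against 0.1647 printed in 5.5 and 16.3% in 5.7.
- Recruitment: 618/0.95 = 650.5, rounded up to 651 per group; 2 × 651 = 1302.

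The printed numbers are correct for the 309+309 plan.

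**Step 2: list the outcomes of the 5.6 rule.** Write p for the superiority p-value and t for the confidential threshold.

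| Interim result | Second stage | Evaluable total |
|---|---|---|
| either one-sided p ≤ 0.0015 | 0 | 618 |
| continuing, p ≤ t | 500 | 1118 |
| continuing, p > t | 800 | 1418 |

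A continuing trial has either p ≤ t or p > t, so these rows cover every case for any t. A second stage of 618 cannot occur. As a check, the rule was simulated for assumed thresholds from 0.02 to 0.5, because the true value is withheld. At 14% versus 20% the trial ended at 1118 in 31% to 82% of runs and at 1418 in 2% to 53%. It never ended at 1236.

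**Step 3: differences in evaluable patients.**
- 1236 − 1118 = 118 too many for the smaller branch.
- 1418 − 1236 = 182 too few for the larger branch.
- 1418 − 1302 = 116: the larger branch exceeds the recruitment total with no loss at all.

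**Step 4: recruitment by the method of 5.5 (5% loss, rounded up per group).**
- 1118 evaluable: 559/0.95 = 588.4, so 589; 2 × 589 = 1178.
- 1418 evaluable: 709/0.95 = 746.3, so 747; 2 × 747 = 1494.

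Rounding the total instead gives 1177 and 1493. Both conventions reproduce 1302 (1236/0.95 = 1301.05), so the new totals should be read as approximate.

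**Step 5: which plan 5.7 describes.** Average total = 618 + 500 × (1 − stop rate) + 300 × P(1418). At 14% versus 20%:

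P(1418) = (1145.1 − 618 − 500 × 0.837)/300 = 108.6/300 = 0.362, and P(1118) = 0.837 − 0.362 = 0.475.

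The table in 5.7 also shows a maximum of 1418. It describes the rule in 5.6 and not the 1236-patient plan.

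**The case against.** The best defence is that 1236 is a planning size. Section 5.5 makes it conditional and points forward to the recalculation. Section 5.6 prints both real totals, 5.7 shows the range from 618 to 1418, and second-stage recruitment runs on evaluable counts. A careful reader can tell which rule governs, no stopping or testing decision uses 1236 or 1302, and the SAP never calls 1302 a cap. All of this stands, and it limits the consequence to the stated figures. It does not rescue the text: the condition attached to 1236 is one the rule never meets, and the sentence on 1302 carries no condition.

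A second argument is that recruitment may be raised for missing data, so 1302 recruits could accompany 1118 evaluable patients. That would need a loss of 1 − 1118/1302 = 14.1%, against the plan's own limit of 5%. It cannot help the larger branch, where 1418 exceeds 1302 with nothing missing.

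A third point is that section 5.3 times the interim at half the total, which fits only 1236: 618 is 55.3% of 1118 and 43.6% of 1418. This is fair, and it is a reason to say in 5.5 that the information rate of 0.5 belongs to the reference plan.

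Finally, the branch shares in step 5 are not needed for the argument, and they bear on a threshold that 5.6 keeps confidential. They follow from printed figures, but they should not be added to the SAP.

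**Conclusion.** The concern holds. The final size of 1236 in 5.5 is unreachable under 5.6, and 1302 is not the planned recruitment of either branch at the stated loss. The reachable evaluable totals for a continuing trial are 1118 and 1418, which differ from 1236 by −118 and +182. The corresponding recruitment is about 1178 or 1494, against 1302 printed.

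That 1236 is unreachable follows from the rule alone and needs no assumption about the threshold. The recruitment totals assume 5% loss, as in 5.5, and per-group rounding.

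This is an inconsistency between two sections and not a miscalculation. The bounds, the type I error (with the combination weights kept fixed at the reference plan) and the power in 5.7 are unaffected. It should be corrected because a confirmatory adaptive design ought to state its possible final sizes consistently.

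**What to change.** In 5.5, replace the sentence on the unadjusted final analysis and the sentence on 1302 recruits with:

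> The reference plan (309+309 per group, 1236 evaluable, 1302 recruited at 5% loss, power 80.1%) sets the decision bounds and the information rate of 0.5. Under the rule in 5.6, a trial that continues after the interim analysis ends with 1118 or 1418 evaluable patients. At 5% loss this corresponds to a planned recruitment of about 1178 or 1494 patients, which may be increased to compensate for missing data (5.6). The power of the applied rule is given in 5.7 (82.1% at 14% versus 20%).

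Give no fixed recruitment cap, since 5.6 works with evaluable counts and leaves recruited numbers open.

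The cost is two sentences. No patients are added beyond what 5.6 already commits to. The bounds, the interim threshold of 0.0015, the second-stage sizes and the confidential threshold stay as they are.
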